#### **9.5.5 Storage**

Before preparation for use, pegloticase will be stored in the carton, maintained under refrigeration between 2°C and 8°C (36°F and 46°F), protected from light and will not be shaken or frozen.

Pegloticase diluted in infusion bags is stable for 4 hours at 2°C to 8°C (36°F to 46°F) and for 4 hours at room temperature (20°C to 25°C, 68°F to 77°F).

MTX will be stored between 20°C to 25°C (68°F to 77°F) [See USP Controlled Room Temperature] and protected from light.

### **9.5.6 Drug Accountability**

Clinical supplies will be dispensed only in accordance with the protocol. Accurate records of the clinical supplies received, the amount dispensed for each subject and the amount remaining at the conclusion of the study will be maintained. Each study site will also maintain subject drug logs/electronic logs to account for MTX dispensed and subject compliance will be monitored by the site at each visit (see Section 9.5.11).

Subjects will bring the MTX dosing calendar to each study visit for assessment of compliance. Subjects will bring the MTX bottle to each visit for a compliance check by the site. The site will manually count the pills and re-dispense the bottle to the subject. At the end of the study or if the subject prematurely discontinues the study, the subjects will return any unused or partially used study drugs to the site.

Investigational clinical supplies will be received by a designated person at the study site, handled and stored safely and properly and kept in a secured location to which only the Investigator and designated assistants have access.

Please reference the Study Pharmacy Manual for more detailed information on MTX and pegloticase packaging, labeling, storage and destruction.

### **9.5.7 Study Drug Administration and Timing of Dose for each Subject**

#### **9.5.7.1 Description of Clinical Supplies**

PCI Pharma Services will supply study drugs (pegloticase and MTX) to clinical sites. Ancillary supplies for dosing will be provided by the study site (i.e., infusion bags containing normal saline, syringes, needles, alcohol swabs, gauze pads, bandages and biohazard containers for safe storage of used needles and syringes).

#### **9.5.7.2 Determination of Dose Volume**

Pegloticase will be administered as an admixture of 8 mg in 50 mL of 0.45% or 0.9% Sodium Chloride Injection, United States Pharmacopeia (USP) for IV infusion. Alternatively, pegloticase is administered as a ready-to-use solution with 8 mg uricase formulated in 50 mL phosphate-buffered saline that is suitable for IV infusion.

In the event of an IR, the infusion should be slowed, or stopped and restarted at a slower rate at the discretion of the Investigator. Modifications to the infusions at subsequent visits following an IR can be discussed with Medical Monitor.

### **9.5.7.3 Details Concerning Timing and Dose Administration**

#### **9.5.7.3.1 Preparation and Administration**

##### **9.5.7.3.1.1 Preparation**

###### **8 mg/mL Uricase:**

Vials of pegloticase will be visually inspected for particulate matter and discoloration before administration, whenever solution and container permit. Vials should not be used if either is present. Using appropriate aseptic technique, 1 mL of pegloticase will be withdrawn from the vial into a sterile syringe. Any unused portion of product remaining in the vial will be discarded. Syringe contents will be injected into a single 50 mL bag of 0.45% or 0.9% Sodium Chloride Injection, USP for IV infusion and will not be mixed or diluted with other drugs. The infusion bag containing the dilute pegloticase solution will be inverted a number of times to ensure thorough mixing but will not be shaken. In accordance with good pharmacy practice, gloves will be worn during preparation of the dose.

Pegloticase must be started within 4 hours of dilution. Before administration, the diluted solution of pegloticase will be allowed to reach room temperature. Pegloticase must never be subjected to artificial heating.

###### **0.16 mg/ml Uricase:**

Vials of pegloticase of the alternative ready-to-use presentation (50 mL) will be visually inspected for particulate matter and discoloration before administration, whenever solution and container permit. Vials should not be used if either is present.

Before administration, allow the solution of pegloticase to reach room temperature. Pegloticase must never be subjected to artificial heating.

##### **9.5.7.3.1.2 Dose and Administration**

###### **Methotrexate**

All subjects will take oral MTX at a dose of 15 mg weekly.

###### **Folic Acid**

All subjects will take folic acid 1 mg orally daily. Folic acid will be supplied by a local pharmacy.

###### **Pegloticase**

All subjects will receive pegloticase at a dose of 8 mg administered IV every 2 weeks for a total of 12 infusions from Day 1 through Week 24, inclusive (Pegloticase + MTX Period). Subjects will not be fasting on the day of infusion and will be encouraged to have a snack or normal meal

before or after the infusion. Pre-infusion SUA results must be reported by the local or central laboratory prior to pegloticase infusion (see Section 9.6.2.1).

Standardized IR prophylaxis consisting of pre-treatment with antihistamines, acetaminophen and corticosteroids will accompany each infusion (see Section 9.5.2.3).

Pegloticase will be administered either as a ready-to-use 0.16 mg/mL IV solution (50 mL) or an admixture of 8 mg in 50 mL of 0.45% or 0.9% Sodium Chloride Injection, USP for IV infusion by gravity feed or infusion pump. After approximately 30 subjects in 30 min cohort receive admixture of 8 mg in 50 mL of 0.45% or 0.9% Sodium Chloride Injection, USP for IV infusion, newly enrolled subjects will be assigned to ready-to-use 0.16mg/mL IV solution (50 mL). Pegloticase will not be administered as an IV push or bolus.

In a patient with IV site, using tubing with no in-line filter, the pegloticase preparation will be infused over approximately 30 to 60  $\pm$ 5 minutes, depending on cohort assignment, while the subject is under close observation for any signs of distress. If an in-line filter is used, it should be 0.2  $\mu$ m or larger. At the end of the infusion, the IV line will be flushed with 10 mL of normal saline to ensure the full dose is administered. The date and time of infusion start and stop (inclusive of the IV flush) will be recorded.

### **9.5.7.3.2 Dose Modifications, Interruptions and Delays**

#### **9.5.7.3.2.1 Pegloticase Modifications**

Administration of pegloticase will be immediately held if the subject experiences any significant IR such as respiratory distress, agitation, chest or back pain, urticaria, or another clinically significant event occurring during infusion. If the AE meets the definition of an SAE for IR, the infusion should not be restarted unless the site Investigator determines it is safe to resume the infusion. If the AE does not meet the definition of an SAE for IR, the site Investigator may make the decision to re-start the infusion depending upon the nature and severity of the AE.

Infusions subsequent to an IR in an individual subject may be given in a larger volume of diluent, not to exceed 500 mL. In this case, the infusion duration will also be extended to a minimum of 3 hours. The total volume and duration of infusion will be captured in the medical record and eCRF.

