## 9.2 Infusion Speed-Limiting Criteria

Infusion speed-limiting criteria will be met if a subject experiences any severe (Grade  $\geq 3$ ) IRs or any other severe AEs within 24 hours of receiving pegloticase infusion and attributed to the infusion and not any other underlying disease process. The signs and symptoms of the severe IRs are usually prolonged (e.g., not rapidly responsive to symptomatic medication and/or brief

interruption of infusion) or recurrent following initial improvement. Possible associated signs and symptoms of IRs may include but not limited to:

- Respiratory: difficulty breathing with wheezing or stridor; upper airway swelling (lip, tongue, throat, uvula, or larynx); respiratory distress manifested as at least 2 or more of the following: tachypnoea, increased use of accessory respiratory muscles, cyanosis, recession, grunting
- Cardiovascular: hypertension, tachycardia, measured hypotension, a decreased level of consciousness, loss of consciousness
- Dermatological or mucosal: generalized urticaria (hives) or generalized erythema, angioedema, generalized pruritus with skin rash

If  $\leq$  one-eighth of subjects meet infusion speed-limiting criteria at the same infusion duration after 3 subjects and after 6 subjects, then enrollment may continue at the same infusion duration. If  $\leq$  one-third of subjects meet infusion speed-limiting criteria at the same infusion duration after 10 subjects, then enrollment may continue at the next progressively shorter infusion duration.

If  $>$  one-eighth of subjects meet infusion speed-limiting criteria, then enrollment at that infusion duration may be suspended.

Safety Review Committee must confirm that infusion speed-limiting criteria were met, prior to additional patients being enrolled at the previous infusion duration. In the event that  $>$  one-eighth of subjects meet infusion-speed limiting criteria at the initial 60-minute infusion duration, then the study may be revised or terminated (after internal review and assessment).

If an anaphylaxis event occurs in any subject, further dosing with pegloticase for that subject will be terminated.

If any anaphylaxis event or SAE related to pegloticase infusion occurs with any subject, all pertinent data will be provided for expedited review to the Adjudication Committee (for the purpose of adjudicating AESIs) and the SRT/SRC.

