#### **9.5.7.3.2.4 Infusion Reaction Treatment**

Subjects must be monitored closely for signs and symptoms of IRs. In the event of an IR, the infusion should be slowed, or stopped and restarted at a slower rate at the discretion of the Investigator. If a serious IR occurs, the infusion should be discontinued and treatment should be provided, as needed.

If a subject experiences an AE suspected to be an IR:

- A physical examination will be performed to capture medically relevant details, including, but not limited to, a thorough dermatologic examination for detection of erythema, urticaria (hives), or peri-oral or lingual edema; a chest examination for breath sounds, stridor or wheezing; and a cardiac examination with attention to irregular heartbeat.
- Vital signs (sitting or supine BP, heart rate, respiratory rate and body temperature) will be captured at least every 30 minutes until the resolution or stabilization of the AE.
- A 12-lead ECG will be performed.
- A serum sample will be collected in a serum-separating tube at that time or at the subsequent visit. The sample will be centrifuged, frozen at -20°C or colder and stored for the batch shipment to a Horizon designated laboratory for evaluation of pegloticase antibodies at a future date.

If, in the Investigator's opinion, the subject is experiencing an anaphylactic reaction (see Section 9.6.1.2.1.5), pegloticase should be immediately discontinued. Any incidence of anaphylaxis should be reported as an SAE.

The Investigator may administer any medically indicated pharmacologic agent or procedure intended to relieve symptoms (CAUTION: no other drugs can be mixed in the pegloticase infusion bag). Signs and symptoms of the AE and drugs given for treatment are to be recorded in the medical record and in the eCRF.

After the first incidence of an IR that does not meet the criteria of anaphylaxis (see Section 9.6.1.2.1.5) or does not meet serious criteria, the Investigator may elect to initiate the next infusion at a slower rate. Additionally, the Investigator may choose to prescribe prednisone (e.g. 20 mg) to be taken in the morning of the next infusion. All changes to infusion rate or dilution and drugs given for prophylaxis or treatment, are to be recorded in the medical record and in the eCRF.

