#### **9.7.1.2 Secondary Endpoints**

The secondary endpoints will be assessed for the cohort chosen to be the most desirable duration for infusion and include:

- The proportion of Month 6 (Weeks 20, 22 and 24) responders, defined as subjects achieving and maintaining sUA <6 mg/dL for at least 80% of the time during Month 6.
- The proportion of subjects who experienced any of the following events: IR leading to discontinuation of treatment, anaphylaxis, or meeting Individual Subject sUA Discontinuation Criteria.
- Time to any of the following events: IR leading to discontinuation of treatment, anaphylaxis, or meeting Individual Subject sUA Discontinuation Criteria (two consecutive pre-infusion sUAs > 6 mg/dL).

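### The protocol gives conflicting instructions for the ongoing infusion after a serious infusion reaction, and the one that permits resumption makes no exception for anaphylaxis

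*Protocol*

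**What the plan says.** On the ongoing infusion:

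- **Protocol 9.5.7.3.2.1 (Pegloticase Modifications).** The infusion is held for a significant reaction. If the event meets the SAE definition, "the infusion should not be restarted unless the site Investigator determines it is safe to resume the infusion". If it does not, the investigator may also decide to restart. Anaphylaxis is not mentioned.
- **Protocol 9.5.7.3.2.4 (Infusion Reaction Treatment).** For IRs in general, "the infusion should be slowed, or stopped and restarted at a slower rate at the discretion of the Investigator". The next sentence reads "If a serious IR occurs, the infusion should be discontinued and treatment should be provided, as needed". If the investigator believes the reaction is anaphylactic, "pegloticase should be immediately discontinued. Any incidence of anaphylaxis should be reported as an SAE".
- **Protocol 9.5.7.2 (Determination of Dose Volume).** The general option to slow, or to stop and restart, is repeated for any IR without a split by seriousness. Changes at later visits can be discussed with the Medical Monitor.
- **Protocol 9.2, and the synopsis under the same heading.** "If an anaphylaxis event occurs in any subject, further dosing with pegloticase for that subject will be terminated".

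On later infusions:

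- 9.5.7.3.2.1 says "Infusions subsequent to an IR in an individual subject may be given in a larger volume of diluent, not to exceed 500 mL", with no limit by seriousness.
- 9.5.7.3.2.4 addresses a first IR that is not anaphylaxis or, in the words that follow, "does not meet serious criteria, the Investigator may elect to initiate the next infusion at a slower rate".

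On the endpoints, the secondary composite in protocol 9.7.1.2 and SAP 3.4.2.2 consists of "IR leading to discontinuation of treatment, anaphylaxis, or meeting Individual Subject sUA Discontinuation Criteria". It is analysed both as a proportion and as a time to event.

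**The concern.** The infusion reaction is the event this trial is built to measure, and protocol 7.2 itself raises the possibility that shorter infusions increase adverse events. For the most consequential form of that event, the two sections on handling it differ. A site working from 9.5.7.3.2.1 may resume the infusion after a serious reaction if the investigator is satisfied. A site working from 9.5.7.3.2.4 would discontinue it. Both would be following the protocol.

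What is at stake is mainly subject safety: whether someone who has just had a serious reaction receives the rest of that infusion could depend on which page the site consulted. Because the secondary composite includes IRs that end treatment, there is also a question whether uneven handling could reach an endpoint.

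**Working it through.** The plan states no figure on this point, so the check is a comparison of texts.

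**Step 1. The ongoing infusion, by type of reaction.**

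| Reaction | 9.5.7.2 | 9.5.7.3.2.1 | 9.5.7.3.2.4 | 9.2 and synopsis |
|---|---|---|---|---|
| Non-serious IR | Slow, or stop and restart | Hold if significant; investigator may restart | Slow, or stop and restart | No instruction on the infusion |
| Serious IR, not anaphylaxis | As above, no split | No restart unless judged safe | Discontinue; no restart mentioned | Expedited review if an infusion-related SAE; no instruction on the infusion |
| Anaphylaxis | As above, no split | As for any SAE; no exception | Discontinue at once | No further dosing for that subject |

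The first row is consistent. The second and third are not.

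**Step 2. Can discontinued in 9.5.7.3.2.4 mean paused?** That would remove the conflict, with 9.5.7.3.2.1 supplying the condition for resuming. The context is against it. The sentence immediately before already provides for stopping and restarting in IRs generally, and the serious-IR sentence follows as the contrasting case. If it also allowed a restart, it would add little to the sentence before it.

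**Step 3. Anaphylaxis.** Protocol 9.6.1.2.1.5 and 9.5.7.3.2.4 require every anaphylaxis to be reported as an SAE. It therefore meets the condition in 9.5.7.3.2.1, whose resume clause has no carve-out. Read alone, that section leaves resumption open for an event after which three other places (9.5.7.3.2.4, 9.2 and the synopsis) end dosing.

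**Step 4. Later infusions.** Both statements are permissions. 9.5.7.3.2.1 allows a larger diluent volume after an IR, and 9.5.7.3.2.4 allows a slower next infusion. Neither forbids later infusions after a serious IR that is not anaphylaxis. The condition in 9.5.7.3.2.4 joins its two parts with *or*. Read literally, a serious IR that is not anaphylaxis satisfies it; if *and* was meant, it does not. This is an ambiguity.

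**Step 5. Reach into the endpoints.**

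- *Primary endpoint.* It counts subjects with an IR. A subject with a serious IR is already counted, whether or not the infusion resumes.
- *Secondary composite.* Anaphylaxis is a component in its own right, so those subjects count under either reading. That leaves serious IRs that are not anaphylaxis. The handling sections govern one infusion, whereas the component counts the end of treatment. Ending treatment is a separate decision, with its reason recorded under 9.4.3 and 9.4.3.1.
- *Scale.* At the planning rate in 9.7.9, expected subjects with any IR are 0.05 × 110 = 5.5, anaphylaxis included. One subject changing status would move a proportion by 1/110 = 0.9 percentage points. The documents do not give the number of serious IRs, nor the share whose treatment status would follow from how one infusion was handled, so the calculation stops here.

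**The case against.** The best defence is that the two sections share a default, which is not to continue after a serious IR, and that 9.5.7.3.2.1 merely adds an investigator exception. Anaphylaxis is settled elsewhere in the protocol, and any infusion-related SAE goes to expedited review by the Adjudication Committee and the safety review bodies (9.2). The eCRF already records the reason for stopping study drug, and the SAP summarises interrupted infusions and events leading to permanent withdrawal of pegloticase.

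Much of this stands. It confines the truly open case to serious IRs that are not anaphylaxis, and it means no new data collection is needed. It does not remove the conflict. An exception that appears in one section and is absent from the section headed as treatment of infusion reactions is not a single instruction. Expedited review follows the event and does not tell the site what to do with the infusion in progress. The anaphylaxis rule exists, but the resume clause neither refers to it nor exempts it.

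Two stronger readings are tempting, and the documents do not support them:

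- A reader might infer that the sections also contradict each other on later infusions. They do not: two permissions and an unclear *or* are not opposing instructions.
- A reader might infer that the secondary result depends on which section a site follows, for example that 1 to 3 serious IRs would shift the component by 0.9 to 2.7 points (1/110 to 3/110). That range assumes a serious-IR count the documents do not give. It also assumes that each such subject's treatment status switches with the handling of one infusion, which neither document says.

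**Conclusion.** The concern holds for the ongoing infusion. After a serious IR, 9.5.7.3.2.1 and 9.5.7.3.2.4 cannot both be followed as written when an investigator judges resumption safe, and 9.5.7.2 adds general wording that ignores seriousness. The resume clause also covers anaphylaxis by its terms, against the protocol's own rule elsewhere. This is an internal inconsistency bearing on subject safety, and it should be corrected.

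Its statistical consequence is limited. The primary endpoint, the sample-size statement and the 13% criterion in SAP 3.4.1 do not depend on it. Any effect on the composite is indirect, runs only through serious IRs that are not anaphylaxis, and cannot be quantified from the documents. The conclusion rests on reading discontinued in contrast with the stop-and-restart sentence before it. Even on the softer reading, the missing exception for anaphylaxis and the unclear *or* remain.

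**What to change.** Reconcile protocol 9.5.7.2, 9.5.7.3.2.1 and 9.5.7.3.2.4 with 9.2 and the matching synopsis text:

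1. Give one instruction for the ongoing infusion after a serious IR, stated once and cross-referenced from the other sections.
2. Align the resume clause in 9.5.7.3.2.1 with the anaphylaxis rule the protocol already sets in the synopsis, 9.2 and 9.5.7.3.2.4. As those sections stand, this means an explicit exception.
3. State in 9.5.7.3.2.4 whether its two conditions for a slower next infusion are alternatives or must both hold.

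Which clinical rule applies to a serious IR that is not anaphylaxis is for the sponsor to decide. The cost is protocol wording at the next amendment and a short memo to sites, with no change to sample size, data collection or analysis.

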#### **9.5.7.3.2.2 MTX Dose Algorithm and Intolerance Criteria**

During the MTX Run-in a subject will be considered a screen failure if any of the following new laboratory findings or symptoms reflecting MTX intolerance occur:

1. Abnormal Hematology findings:
  - a. WBC  $< 3.5 \times 10^9/L$
  - b. Platelets  $< 75 \times 10^9/L$
  - c. Hematocrit  $< 32\%$
2. Abnormal hepatic function findings:
  - a. AST/ALT  $> 1.5 \times$  upper limit of reference range and

- b. Albumin < lower limit (LLN) of reference range
3. Abnormal renal function: eGFR <30ml/min/1.73 m^2 (as estimated with the MDRD equation).
4. New clinically important signs and symptoms, such as the following:
  - a. Rash or oral ulceration
  - b. Persistent nausea, vomiting and diarrhea
  - c. New or increasing dyspnea or dry cough, or unexplained cough with fever
  - d. Severe sore throat, abnormal bruising
  - e. Severe headaches, fatigue and problems concentrating

Note that if minor clinical symptoms emerge, such as mild stomatitis, mild GI discomfort, etc., the investigator may increase folic acid dose (e.g. 2 mg daily) or recommend a divided dose of MTX (e.g. 3 tabs of 2.5 mg in the morning and evening on the day of dosing); if symptoms improve, subject will not be considered a screen failure on the basis of that symptom.

During the Run-In and Pegloticase + MTX Period, MTX dose guidance based on new laboratory findings or new symptoms is as follows:

Lab Parameters	Value	MTX Dose Change
WBC	3.0 x 10  /L ~ 3.5 x 10  /L	Decrease to 10 mg
	< 3.0 x 10  /L	Temporary stop
Platelets	< 50 x 10  /L	Temporary stop
Hematocrit	< 27%	Temporary stop
AST/ALT	Between 1.5 ~ 2 x ULN	Decrease to 10 mg
	> 2 x ULN	Temporary stop
eGFR	< 30 ml/min/1.73 m 	Temporary stop
New clinically important symptoms/signs*	Yes	Temporary stop

\* New clinically important symptoms or important medical events:

- a. Rash or oral ulceration
- b. Persistent nausea, vomiting and diarrhea
- c. New or increasing dyspnea or dry cough, or unexplained cough with fever
- d. Severe sore throat, abnormal bruising
- e. Severe headaches, fatigue and problems concentrating

- f. Any other important medical events that might increase methotrexate toxicity or pre-dispose to new or worsening infection (e.g. undergoing surgery, hospitalization, being treated with antibiotics, having a clinical infection, developing new clinically significant pericardial / pleural effusion or ascites)

Note that if minor clinical symptoms emerge, such as mild stomatitis, mild GI discomfort, etc., the investigator may increase folic acid dose to 2 mg daily or recommend a divided dose of MTX (e.g. 3 tabs of 2.5 mg in the morning and evening on the day of dosing) and monitor for symptom resolution.

Investigators should discuss the emergence of any one of the following criteria with the medical monitor to review the case:

1. ALT/AST  $> 1.5 \times$  ULN on 3 of any 5 consecutive measures
2. Albumin  $< 0.8 \times$  LLN on 2 consecutive measures
3. Any laboratory or clinical symptoms leading to temporary stop on 3 consecutive measures, in which case the medical monitor will review to consider re-initiation, a continued temporary stop, or a permanent stop in discussion with the PI.

Guidance for increasing MTX back towards 15 mg after dose reduction, based on improvement or resolution of abnormal liver enzymes ( $> 2 \times$  ULN):

1. When liver enzymes return to values  $\leq 1.5 \times$  ULN, increase MTX or dose by 2.5 mg and reassess in 2 weeks.
2. If liver enzymes remain  $\leq 1.5 \times$  ULN, increase MTX or dose by 2.5 mg and reassess in 2 weeks.

Improvement of other laboratory abnormalities potentially attributed to MTX or may also warrant titration back up to 15 mg weekly, based on Investigator judgement and in discussion with the Sponsor medical monitor.

